**Methods:** . Adult, female patients (≥18 years) with ER+ MBC (Stage IV) of any race/ethnicity will be recruited from within and around LUMC. Women with a serum 25(OH)D <30 mg/dl will be invited to participate in an 8 week “proof of concept” study. Following current clinical practice guidelines, eligible participants will receive 50,000 IUs of vitamin D3 weekly for 8 weeks. Laboratory values (e.g., serum 25(OH)D, calcium, , serum estradiol), muscle function and inflammatory biomarkers (e.g.,CRP) will be examined pre- and post-supplementation, while symptoms (pain, sleep, fatigue, mood, and overall quality of life) will be assessed at baseline, 4 and 8 weeks post-supplementation. We will assess if increases in serum 25(OH)D are associated with clinically significant changes in serum estradiol, improvements in symptoms and QOL, and decreased inflammation, controlling for sunlight exposure, diet, physical activity and body composition. Women with a serum 25(OH)D ≥ 30 mg/dl who do not require supplementation will be invited to complete the study questionnaires at baseline.

**Significance/Impact:** Vitamin D3 may be a cost-effective, adjuvant therapy to combat the side-effects of treatment, to increase medication adherence and to enhance supportive care in this unique population in need of evidence-based strategies. These findings will help to characterize symptom burden in this growing population and to demonstrate the feasibility of this clinical trial. Ultimately, these data will provide novel, preliminary data to justify a larger randomized trial.

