## **V. Study Design**

**a. Research design:** This study is comprised of an intervention arm (Group 1) and non-intervention arm (Group 2). For eligible women with low serum levels of vitamin D, we propose an 8 week open label, single arm “proof of concept” study to address concerns regarding vitamin D3 dosing, to monitor important laboratory parameters and to assess potential effects on short-term outcomes. While a randomized controlled trial (RCT) has been the traditional model to evaluate the efficacy of vitamin D supplementation, this design may be considered premature until the safety of this therapy has been evaluated in a patient population with the potential for high clinical acuity. For the women who meet all eligibility criteria except they have normal serum levels of vitamin D (Group 2), we will assess their symptomology and test associations with the biomarkers of inflammation.

**b. Study population:** Adult females with ER+ MBC can participate in the present study provided they are under the care of medical oncologist and meet all eligibility criteria. Women with early stage disease (Stages 0-3) or women with MBC who are ER- are unable to participate in this study.

**c. Sample size and power considerations:** Because this is a pilot project that will assess the feasibility, preliminary safety and short-term efficacy of a vitamin D3 intervention in this population, typical sample size calculations will not be employed. We will assess symptoms at baseline for all participants to establish prevalence estimates and at three time points in the intervention group to help increase our abilities to detect changes over time. Because of the high prevalence of vitamin D deficiency among breast cancer survivors (~75%) and the high volume of patients seen at LUMC and by [name] (collaborator), we anticipate that we can successfully recruit and enroll 50 women who meet the eligibility criteria. Our goal is to recruit 25 women for the intervention arm. Factoring in an attrition rate of ~20%, we should have complete data on 20 women who complete the intervention. This sample size is sufficient to demonstrate feasibility and will allow for the generation of effect size and variance estimates, as well as confidence interval widths around these estimates for future applications.

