### Inclusion Criteria:

1. Metastatic breast cancer (Stage IV)
2. Histologically confirmed estrogen receptor positive disease
3. Female
4. Serum 25(OH) <30 ng/ml
5. Age  $\geq$  18 years
6. Pre or post-menopausal
7. ECOG Performance status 0-2
8. Adequate organ function as defined as GFR > 30 mls/min and serum calcium  $\leq$  10.4 mg/dl
9. Any race/ethnicity
10. English speaking
11. No changes to MBC treatments within 30 days of enrollment and/or deemed clinically stable by their treating physician
12. Willingness to sign a written informed consent and complete questionnaires
13. Cease ingestion of vitamin D supplementation not study related

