**v. Study intervention:** Following the clinical practice guidelines of the Endocrine Society, participants in Group 1 will receive 50,000 IU of vitamin D3 once a week for 8 weeks. This dose of vitamin D3 is similar to those used in other breast cancer trials involving women with Stage 0-III disease, and should be sufficient to increase levels in normal weight, overweight and obese women within an 8 week time frame. In addition, weekly dosing will also help to increase study compliance and participants will receive a weekly reminder (phone call, email or text) to take their supplement. Because this is a single arm, open label trial, all participants will be aware that they are taking the study medication and that no placebo is being offered in this trial. Participants will be encouraged to take less than 1000 mg/d of calcium supplementation and to emphasize food sources of calcium (see calcium handout in the appendices). Participants in the non-intervention arm (Group 2) will complete all of the baseline (Week 0) study questionnaires and physical measures.

**vi. Study assessments and activities:** Guided by the Wilson and Cleary health-related QOL model, we will examine seven levels of patient outcomes, including: a) biological and physiological, b) symptom status, c) functional status, d) health perceptions, e) overall QOL, and f) characteristics of the individual and the environment. Variables, measures and times are delineated below (Table 1). Brief details about each of the measurement tools are described below.

Table 1. SAFE-D study variable, measures, constructs and timing				
	Variables	Measures	Wilson & Cleary construct	Week
Aim 1	Low vitamin D (Primary)	25(OH)D, calcium, , serum estradiol, CMP	Biological	0,8
Aim 2	General well-being (Secondary) Pain Fatigue Mood Muscle function Performance status Sleep Overall health QOL	Brief Pain Inventory, FACT-Bone pain Piper Fatigue Scale HADS, PHQ8 Hand grip strength ECOG PSQI Single item question FACT-B, FACT-ES	Symptom status Symptom status Symptom status Functional status Functional status Symptom status Health perceptions Overall QOL	0,4,8 0,4,8 0,4,8 0,8 0 0,4,8 0,4,8 0,8
	Serum vitamin d and Inflammation (Exploratory)	CRP, interleukins, TNF- $\alpha$	Biological	0,8

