*Sun exposure:* Because sunlight constitutes the major source of vitamin D, the adult sun habits questionnaire by Glanz et al will be used. Two questions inquiring about summer sun exposure will be used quantify time spent in the sun, which directly correlates with serum vitamin D levels.

*Godin Exercise Leisure-time Questionnaire:* This 4-item tool allows for the quick quantification of time spent engaged in strenuous, moderate or light activities over a typical 7-day period showing reliability coefficients of 0.8 with  $\dot{V}O_2$  measures. A weekly leisure activity score is generated, as well as the frequency of leisurely activities. This tool is recommended and made available by the NCI.

*Medical Outcomes Study Social Support Survey:* The self-administered survey is a 19-item multi-dimensional scale assessing four aspects of social support: tangible support, affectionate, positive social interaction and emotional/informational support (Cronbach’s alphas >0.9 for all subscales.) Total and subscale scores are obtained and compared, with higher scores indicating more support.

**ix. Study completion:** Participants in the intervention will return to LUMC after 8 weeks of supplementation for their final blood analyses (serum 25(OH)D, calcium, , serum estradiol, inflammatory markers), anthropometric and body composition evaluations, pill counts and questionnaire completion. An 8 week intervention was selected because: 1) this timeframe is consistent with the clinical practice guidelines of the Endocrine Society for vitamin D repletion, and 2) it is an efficient and opportune time to assess the effects of vitamin D on biological and symptom outcomes. Participants in the non-intervention arm will not be followed after their baseline visit. They will be considered “complete” after their baseline visit.

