## **VII. Safety Monitoring Plan**

- a.** Published reports suggest that 50,000 IUs of vitamin D taken *daily* can increase vitamin D levels to more than 150 ng/dl and cause hypercalcemia. The proposed dosing for this study is 50,000 IUs per week, which equates to ~7,000 IUs/day. This dose has minimal side-effects in healthy populations, but may include bone pain, constipation, dry mouth, headache, stomach upset and loss of appetite. We will be monitoring laboratory values at baseline and 8 weeks, and patient symptoms at baseline, 4 and 8 weeks.
- i. Any patient who receives treatment on this protocol will be evaluable for toxicity. This study will utilize the CTCAE (NCI Common Terminology Criteria for Adverse Events) Version 4.0 available at (<http://ctep.cancer.gov>). Participants will be called after 4 weeks of supplementation to ascertain pill counts, gauge their general tolerance and capture symptom management data related to pain, fatigue, mood, sleep and overall health. Although toxicity and adverse side-effects from vitamin D3 supplement are rare, participants will be queried their general tolerance to the study medication during the 4 week phone call. The following criteria will be utilized to determine supplement suspension or supplement discontinuation: .If the participant develops Grade 1 toxicity that is felt to be possibly, probably, or definitely related to study supplement, the participant will continue to be monitored.
  - ii. If the participant develops Grade 2 toxicity that is felt to be possibly, probably, or definitely related to study supplement, the participant may go on study supplement holiday until toxicities are Grade 1 or lower (for no longer than 4 consecutive weeks).
  - iii. If a participant develops any Grade 3 or Grade 4 or has persistent Grade 2 toxicity beyond four consecutive weeks possibly, probably, or definitely related to the study supplement, the study supplement will be discontinued. A blood draw at the nearest Quest Diagnostics facility or the Cardinal Bernadin Cancer Center Phlebotomy Laboratory will be procured to obtain 25(OH)D and a comprehensive metabolic profile.

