  - iv. If a participant's serum calcium and corrected calcium\* exceeds 10.5 mg/dL, then study supplement will be suspended. The participant will be encouraged to lower any calcium intake and provided a handout on calcium sources. The serum calcium will be rechecked in two weeks and the participant may continue on study supplement if the serum calcium is below 10.5 mg/dL. Otherwise, the participant will be removed from study intervention. The participant may also be removed from study intervention for any Grade 2 or higher hypercalcemia (serum calcium > 11.5 mg/dl).  
\*Corrected calcium = serum calcium + [(4.0 – serum albumin) x 0.8]
  - v. In each of these cases, the follow up questionnaires and follow-up blood analyses will still be collected as per protocol eight weeks after the initial start of the intervention.
- b.** Participants may be re-challenged following a suspension. Specifically, participants who have had a study physician-ordered dose suspension may be re-challenged by returning to the full dosage, or

the study physician may decide to have the participant continue her participation on a reduced dose (e.g., 25,000 IUs/week) until study completion.

- c. A participant will be taken off study if she experiences any of the following adverse events: 1) hypercalcemia (>11.5 mg/dL), 2) a serum 25(OH)D level >100 mg/dL with normal calcium or symptoms of vitamin D indicating possible toxicity, 3) clinically significant increases in serum estradiol indicating a potential drug-nutrient interaction, or 4) has intolerable side-effects believed to be associated with vitamin D3 supplementation. Serious and/or unanticipated adverse events will be reported to the Loyola IRB within 24 hours of occurrence.
- d. To ensure the safety of participants, we will complete an exhaustive review of all safety measurements employed in this study after 7, 19, and 25 patients are enrolled. This includes examining their laboratory values, adverse event logs, and notifications in order to make a determination about whether the study should continue for all participants or whether the study should terminate.

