### **IX. Other considerations**

**a. Potential benefits of the proposed research and future directions:** Seeking to live as normal a life as possible, including the ability to fulfill roles and maintain relationships, is a goal for many that are negatively affected by MBC. Many patients with MBC have serious concerns, including the fear of dying, declining quality of life, side effects of treatment, the ability to care for family, decreasing physical functioning and care at the end of life. Managing symptoms to maintain an optimum quality of life is the major goal of care in the metastatic setting. Many women with MBC who consume vitamin D take it to 'protect their bones.' This study has the potential to provide preliminary evidence to support that vitamin D levels can improve QOL and enhance survivorship care. Additionally, we will be asking participants to biobank their blood for future studies related to vitamin D. Findings from this study will be used for to design and justify a larger trial.

**b. Timeline:** This study is designed and intended to be completed within 18 months. We anticipate that we can screen, recruit and enroll 25 women in the intervention in months 1-12. We will enroll women in the cross-sectional arm of this study until the intervention is complete. Data entry will be on-going throughout the study with final data collection will conclude in month 14. In month 15, we will complete data entry, conduct data cleaning and begin initial statistical analyses. In months 15-18, we will complete our statistical analyses and prepare these data for grant, manuscript and oral presentation.

**c.** This study completed an IND application and has been issued a "study may proceed" decision by the FDA.

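### The safety reviews are triggered by enrolment without requiring week-8 labs, and the calcium limits do not consistently say whether serum or albumin-corrected calcium governs

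*Protocol*

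**What the plan says.** **Reviews.** Protocol VII.d promises a "review of all safety measurements employed in this study after 7, 19, and 25 patients are enrolled". It covers laboratory values, adverse-event logs and notifications, and ends in a decision to continue or terminate. It gives no calendar date, minimum follow-up, accrual pause or stopping threshold.

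**Laboratory schedule.** Four places agree on two time points:
- Abstract, Methods: laboratory values "will be examined pre- and post-supplementation".
- Table 1 (VI.a.vi), Aim 1 row: "25(OH)D, calcium, , serum estradiol, CMP" at weeks 0 and 8.
- VI.a.ix: women in the intervention "return to LUMC after 8 weeks of supplementation for their final blood analyses".
- VII.a: "We will be monitoring laboratory values at baseline and 8 weeks, and patient symptoms at baseline, 4 and 8 weeks". The week-4 contact is a phone call.

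**Accrual.** IX.b: "We anticipate that we can screen, recruit and enroll 25 women in the intervention in months 1-12". V.c allows for about 20% attrition.

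**Calcium.** Inclusion criterion 8 reads "Adequate organ function as defined as GFR > 30 mls/min and serum calcium" at or below 10.4 mg/dL. Item VII.a.iv suspends the supplement above 10.5, naming the serum and the corrected value joined by *and*. It allows resumption if serum calcium is below 10.5 two weeks later, and allows removal for serum calcium above 11.5. A footnote gives the albumin correction. VII.c repeats 11.5 without saying which calcium is meant.

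The SAP does not mention the safety reviews or the calcium limits.

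**The concern.** V.a defends the single-arm design on the ground that safety must be evaluated before a randomised trial is attempted. The hazards named in section III are hypercalcaemia and a possible rise in oestrogen production. Hypothesis 1 is about serum calcium and estradiol, and VII.c takes a woman off study for a clinically significant estradiol rise. A tolerance call cannot measure estradiol. A review triggered by enrolment alone can therefore reach its decision with on-treatment laboratory results for few of the women it covers.

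The calcium rules raise a second question. Once VII.a.iv treats serum and corrected calcium as two quantities, a limit written only for serum calcium is naturally read as uncorrected. A woman with low albumin can then pass the entry or recheck limit while her corrected calcium is above the level at which the protocol itself considers suspension.

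**Working it through.** **1. Check of the plan's own timing.** 8 weeks = 56/30.4375 = 1.84 months. Accrual of 12 months + 1.84 = 13.84, which agrees with the end of data collection in month 14 (IX.b). The documents give no count of week-8 labs at any review.

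**2. Week-8 labs at each review.** Assumptions: the counts refer to Group 1, accrual is even over T months, and the review is held at the k-th enrolment. Women still inside their 8 weeks = 1.84 × 25/T. Week-8 labs = k minus that number, rounded down, not below 0.

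| Accrual period T | Still inside 8 weeks | Review at 7 | Review at 19 | Review at 25 |
|---|---|---|---|---|
| 6 months | 7.67 | 0 | 11 | 17 |
| 12 months (planned) | 3.83 | 3 | 15 | 21 |
| 18 months | 2.56 | 4 | 16 | 22 |

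Variations at the planned pace, first review:
- *Attrition of 20%:* 3 × 0.8 = 2.4, so about 2 women.
- *Random (Poisson) arrivals at the same mean pace:* median 2, 5th to 95th percentile 0 to 5.
- *Review held later:* 5 of 7 after four weeks, all 7 after eight weeks (before attrition).
- *Counts covering both groups (50 women in 12 months):* the 7th enrols at 7 × 12/50 = 1.68 months, before anyone can reach 1.84, so 0. If half are Group 1, the later reviews have about 5 and 8.
- *Week-4 call:* 28/30.4375 = 0.92 months; 7 − 0.92 × 25/12 = 5.08, so about 5 of 7 have had it.

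**3. What 3 or 7 women can show.** With no events, the upper end of the two-sided 95% interval is 1 − 0.025^(1/n): 70.8% for 0/3 and 41.0% for 0/7.

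**4. Calcium.** Corrected = serum + 0.8 × (4.0 − albumin). The albumin values are assumptions; the documents give none.

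| Albumin | Serum 10.4 corrects to | Serum above which corrected exceeds 10.5 |
|---|---|---|
| 3.5 | 10.8 | 10.1 |
| 3.0 | 11.2 | 9.7 |
| 2.5 | 11.6 | 9.3 |

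At serum 10.4, corrected calcium passes 10.5 once albumin is below 4.0 − 0.1/0.8 = 3.875. Such a woman satisfies criterion 8 and, if she had been suspended, satisfies the recheck.

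**5. The suspension trigger.** If *and* means that both values must exceed 10.5, the lower of the two decides. With albumin below 4.0 the lower value is serum, so the correction never adds a suspension. With albumin above 4.0 it can only block one: serum 10.8 at albumin 4.5 corrects to 10.8 − 0.4 = 10.4, so there is no suspension. If *or* was meant, serum 10.2 at albumin 3.5 (corrected 10.6) would suspend; under the literal wording it does not.

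**The case against.** *The count depends on the reading.* VII.d says after 7 are enrolled, sets no date, and asks for all safety measurements, so waiting for the cohort's labs is a fair interpretation. This stands: 3 is conditional on a review at the 7th enrolment. What remains is that nothing requires the wait.

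*The early review is not empty.* A reader might infer that the first decision would be taken with almost no safety information. The documents do not support that. Adverse-event logs and baseline labs exist, about 5 of 7 women would have had the week-4 call, and discontinuation for toxicity prompts a 25(OH)D and metabolic panel (VII.a.iii).

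*Seven women is still few, and no stopping threshold is defined.* True. The gain is that the review contains the laboratory values the protocol says it will examine; 7 women do not give a precise estimate.

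*The trigger is only loosely worded.* Also true. The authors may have meant *or*, or corrected calcium alone, since otherwise the formula does little. It would be wrong to infer that they intended to switch the correction off. The gap at entry and recheck does not depend on how *and* is read.

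*Corrected 11.6 against the 11.5 limit.* A reader might call this a breach of the removal limit. VII.a.iv defines that limit on serum calcium, so the comparison does not hold. Only the 10.5 trigger names corrected calcium, and it is the proper yardstick.

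*Physicians can intervene.* Exclusion criterion 13, the discussion with the oncologist in VI.a.iv, and the study physician's choice of full or reduced dose after a suspension (VII.b) are real safeguards. None sets a corrected-calcium limit.

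*The affected women may be rare.* The frequency cannot be judged without albumin data. Eligible women are ECOG 0–2 and on unchanged treatment or judged clinically stable.

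**Conclusion.** The point holds in two parts, and both are worth correcting.

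First, the continue/terminate reviews do not require week-8 labs. Under the planned even accrual, counting Group 1 and reviewing at the 7th enrolment, about 3 of 7 women would have them, with 0 to 7 across the readings shown. Counting Group 1 is the more natural reading: the last count, 25, is that group's target and only that group takes the supplement. On it, the second and third reviews are adequately supplied, so the weakness lies in the first.

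Second, the calcium limits do not use one governing value. A woman with low albumin can enter, or be allowed to resume, with corrected calcium above the 10.5 named in the suspension trigger, subject only to physician discretion. How often is unknown. Because no calcium is scheduled during dosing, this bears mainly on entry and on unscheduled values.

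A reader might go further and infer that women are unmonitored between weeks 0 and 8. That is not so: symptom-based holds and discontinuation work throughout. The narrower limitation is that, for women without symptoms, the laboratory-based rules have no scheduled value to act on before dosing ends.

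**What to change.** **(a) VII.d.** Keep the enrolment-triggered reviews. Add a laboratory review once the 7th and the 19th enrolled Group 1 women have reached week 8 or dropped out and results are in. State that the counts refer to Group 1. At the planned pace these fall at about 3.36 + 1.84 = month 5.2 and 9.12 + 1.84 = month 11.0, with about 10 and 22 women enrolled, so the first still precedes about 15 enrolments. Cost: two extra looks at data already collected.

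**(b) Criterion 8, VII.a.iv and VII.c.** Apply each limit (entry 10.4, suspension and recheck 10.5, removal 11.5) to the higher of serum and albumin-corrected calcium. Using corrected calcium alone would loosen the limits when albumin exceeds 4.0: at 4.5, removal would wait for serum 11.5 + 0.4 = 11.9. The higher-of-two rule loosens none. Take albumin from the metabolic panel at weeks 0 and 8, and add it to any recheck. Confirm that the panel is drawn at week 8: Table 1 lists it, but VI.a.vii describes it as a baseline test and VI.a.ix does not name it. Cost: a few women with low albumin who now pass would be excluded or suspended. If the week-8 panel is confirmed, no visit or scheduled draw is added.
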